3 ENDPOINT ANALYSIS

All data collected in this study will be documented using summary tables and subject data listings. Continuous variables will be summarized using descriptive statistics, specifically the mean, median, standard deviation, minimum and maximum, when appropriate.

Categorical variables will be summarized by frequencies and percentages.

Changes from baseline in dosimetric parameters and quality of life parameters will be assessed using a paired t-test or, if not normally distributed, the nonparametric Wilcoxon Signed-Rank test for continuous variables and Chi-Square and/or McNemar's test for dichotomous variables.

Nominal p-values associated with statistical tests will be reported, but no significance level will be applied to the values. No adjustments to nominal p-values are planned since this is a hypothesis-generating study.

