6.4.6 RT Planning and Radiation Treatment

The technique for delivering the external beam treatment will be employed per institutional standard guidelines. Identical treatment planning studies will be performed both before (pre-TraceIT) and after (post-TraceIT) hydrogel injection in each subject. The technique and setup for these two simulation studies should be nearly identical particularly with respect to patient immobilization and respiratory motion management (i.e., active breath-hold method, forced shallow breathing with abdominal compression or real-time tracking and/or gating) and beam arrangement and angle. Planning set-up/parameters for the pre- and Post-injection RT planning will be documented within the CRF.

The initial **minimum target dose** will be 33 Gy in 5 fractions (6.6 Gy per fraction) or an equivalent biologically effective dose if >5 fractions is being delivered. The goal should be that at that the V33Gy for the PTV be at least 95%. CT simulation will be performed with immobilization when possible.

Normal tissue contours will be performed in accordance with the Upper Abdominal Normal Organ Contouring Guidelines recommended by the 2013 RTOG Consensus Panel.

Target dose constraints for OAR include:

Organs at Risk (OAR)	Dose Constraint*
Proximal duodenum, proximal stomach and small bowel	V15Gy<9cc, V20Gy<3 cc, and V35Gy<1cc A duodenal maximum dose of \leq 32 Gy should initially be attempted
Stomach	V12Gy<50% and V35Gy<1cc
Liver	V12Gy<50%
Combined Kidneys	V12Gy<75%;
Spinal Cord	V8Gy<1 cc

*or biologically equivalent dose constraints for >5 fractions

Target coverage, doses to OAR, dose conformity, mean and maximum proximal duodenal dose and dose volume histograms will be documented pre- and post-TraceIT Injection.

6.4.7 Follow-up for Non-Injection Subjects (30 days +7 days or until resolution/stabilization of an adverse event if applicable)

A “Non-Injection” Subject is a subject who was intended to be treated with TraceIT, but in whom TraceIT was unable to be injected. No further image collection is required for these subjects.

- 30 Day Visit to include:
 - Physical assessment: including sitting blood pressure, pulse, temperature and Zubrod Performance Score
 - Assessment of Intestinal Adverse Events documented using CTCAE criteria
 - Other Adverse Events per NCI CTCAE
 - Changes in concomitant medications used to treat intestinal symptoms

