3.1.1 Hypotheses

This is an early feasibility study with an intent to collect information on the procedural characteristics and safety for TraceIT administration within the peri-duodenal space. Therefore, no formal hypothesis tests of primary or secondary effectiveness endpoints have been planned.

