3.2 Secondary Effectiveness Endpoint

The secondary effectiveness endpoints of this study are the radiotherapy benefits evaluated by comparing treatment planning performed at the baseline and post TraceIT administration, which include:

- Ability to maintain safe duodenal dose constraints
- Percent/volume of GTV/PTV receiving prescription dose
- Overall duodenal dose/ dose distribution.

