3.2.1 Statistical Methods

Radiotherapy Benefits will be assessed via comparison RT planning performed at baseline and post-TraceIT administration for MITT and PP population. For both scans, summary descriptive statistics will be presented by assessment (i.e., Pre- vs. Post-TraceIT Administration) for all target volume and dose constraint measurements. The GTV/PTV receiving prescription dose pre- and post-TraceIT will be reported in an additional table. For the post-TraceIT procedure data, the relative reduction from baseline in dose (V15, V20, V35, mean and maximum duodenal dose, etc.) to the duodenum will also be calculated and summarized.

For continuous radiotherapy benefit variables, the paired sample t-test will be used to test for a difference in means between treatment plans.

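### SAP 3 and Protocol 7.2 allow a chi-square test for dichotomous changes from baseline, which are paired within subject; the practical effect is small and conditional

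*SAP*

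**What the plan says.** SAP 3 states that "Changes from baseline in dosimetric parameters and quality of life parameters will be assessed using a paired t-test", or a Wilcoxon signed-rank test where the data are not normally distributed. The same sentence then gives the option for binary data: "Chi-Square and/or McNemar's test for dichotomous variables". Protocol 7.2 has the same rule. Neither document says when each test applies, or whether McNemar's test is asymptotic or exact.

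The design is single-arm. Protocol 6.4.6 says: "Identical treatment planning studies will be performed both before (pre-TraceIT) and after (post-TraceIT) hydrogel injection in each subject".

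The first secondary endpoint in SAP 3.2 is "Ability to maintain safe duodenal dose constraints". The documents do not say whether it is scored met or not met. SAP 3.2.1 names a test for one type of variable only: "For continuous radiotherapy benefit variables, the paired sample t-test will be used to test for a difference in means between treatment plans". A binary version of the endpoint would therefore fall back on the general sentence in SAP 3.

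On inference, SAP 3.1.1 says that "no formal hypothesis tests of primary or secondary effectiveness endpoints have been planned", and SAP 3 adds: "Nominal p-values associated with statistical tests will be reported, but no significance level will be applied to the values".

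**The concern.** Every variable covered by the sentence is a within-subject change. For continuous data the sentence offers only paired methods; for binary data it adds an unpaired one. With no second arm, there is no independent group for chi-square to compare.

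The analyst could run chi-square in two ways, and neither tests whether the proportion changed. What is at stake is a reported nominal p-value that depends on an unguided choice between a test that suits the data and one that does not.

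**Working it through.** The documents give no outcome data and no derived sample size, so there is no planned figure to reproduce. The counts below are illustrations.

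**Inputs.** n = 6 pairs (SAP 3.1.2), one plan before and one after injection per subject (Protocol 6.4.6). Binary scoring of the first secondary endpoint is an assumption. Let a = met in both plans, b = met only after, c = met only before, d = met in neither. Then pre = a + c, post = a + b, and s = pre + post.

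**Formulas (no continuity correction).**
- Stacked chi-square: X² = 12(post − pre)² / [s(12 − s)]. Since post − pre = b − c, this equals (b − c)² / V with V = s(12 − s)/12.
- Asymptotic McNemar: (b − c)² / (b + c).
- Exact McNemar: two-sided binomial on b + c with probability 0.5.

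The two chi-square-type statistics share a numerator. The stacked version replaces the observed number of discordant pairs by a quantity that depends only on the margins. That is how the pairing is lost.

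**Expected counts.** The smallest is min(s, 12 − s)/2, so it cannot exceed 3.

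**Example, 0/6 to 4/6** (b = 4, c = 0, s = 4).
- Stacked: 12 × 16 / (4 × 8) = 6.0, p = 0.014.
- Asymptotic McNemar: 16/4 = 4.0, p = 0.046.
- Exact McNemar: 2 × 0.5⁴ = 0.125.

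The step from 0.014 to 0.046 is the pairing. The step from 0.046 to 0.125 is asymptotic versus exact, a choice between two paired tests.

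**Same margins, different pairs: 1/6 to 5/6.** Stacked: 12 × 16/36 = 5.33, p = 0.021 however the pairs fall. Asymptotic McNemar gives 0.046 if the discordant split is 4 to 0, and 0.102 if it is 5 to 1 (16/6 = 2.67).

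**The difference can run the other way: 2/6 to 4/6 with b = 2, c = 0.** Stacked: 12 × 4/36 = 1.33, p = 0.25. Asymptotic McNemar: 4/2 = 2.0, p = 0.16.

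**Pre cross-tabulated against post.** X² = 6(ad − bc)² / [(a + b)(c + d)(a + c)(b + d)]. If nobody changes and both outcomes occur, b = c = 0 and X² = 6, p = 0.014. A small p-value then accompanies no change at all. This happens in 5 of the 7 no-change tables; the other 2 are undefined.

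**All 84 possible paired tables at n = 6**, with 0.05 used only as a yardstick:

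| Test | Tables with p < 0.05 |
|---|---|
| Stacked chi-square | 18 |
| Asymptotic McNemar | 12 |
| Exact McNemar | 2 |

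Pairing accounts for 6 of the 16 tables lost, and the exact version for 10.

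**Null rejection at 0.05**, by exact enumeration, with assumed met-probabilities of 0.3 to 0.7 and assumed within-pair correlations:

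| Correlation | Stacked chi-square | Asymptotic McNemar |
|---|---|---|
| 0 | 0.058–0.068 | 0.023–0.036 |
| 0.3 | 0.028–0.030 | 0.008–0.013 |
| 0.6 | 0.007 | 0.001–0.002 |

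**The case against.** The strongest reply is that the clause may never be used. Quality-of-life scores are assigned a paired t-test or Wilcoxon test (Protocol 7.6.4, SAP 3.3.1), and the dose measures named in SAP 3.2.1 are continuous. The wording permits chi-square without requiring it, and names McNemar's test beside it. No significance level is set, no formal test is planned, and with about six subjects the listings will show every pair. All of this stands, and it limits the weight of the point. It does not make chi-square suitable for a paired change.

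A reader might infer three stronger things that the documents do not support.

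- **That chi-square inflates false positives here.** It exceeds 0.05 only modestly at zero correlation and is conservative at 0.3 and 0.6. The fault is that it ignores the pairing and leans on a large-sample approximation.
- **That the whole gap from 0.014 to 0.125 is the error.** In absolute terms, about 0.08 of the 0.11 is asymptotic versus exact McNemar.
- **That the relative reduction in V35 (SAP 3.2.1) is a further error because it is undefined at a 0 cc baseline.** A 5-fraction baseline plan that achieves the 32 Gy duodenal maximum first attempted (Protocol 6.4.6) would have V35 = 0 cc. But the number of such subjects is unknown (0 to 6), and plans with more than 5 fractions use equivalent constraints. SAP 3.2.1 already gives pre and post summaries "for all target volume and dose constraint measurements" and a paired t-test, with relative reduction as an addition. SAP 7.3 leaves calculation rules to code or footnotes. This is missing detail.

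**Conclusion.** The point holds as an error of wording: one of the two tests named for binary changes from baseline does not test change in this design. I would correct it, but nothing in the sample size, the primary endpoint or any decision rule depends on it.

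The practical effect arises only if a binary change is analysed, and the constraint endpoint scored met or not met is the one evident candidate. In that case the nominal p-value can differ by a factor of about three between stacked chi-square and asymptotic McNemar (0.014 against 0.046 in the example), in a direction that depends on the pairs.

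The figures assume six pairs. Replacement (Protocol 6.5) and the exclusion of technical failures from the MITT population (SAP 4.1.2) could change that number.

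**What to change.** - In SAP 3, remove the chi-square option and leave McNemar's test. The exact version is sensible at about six pairs.
- Show the paired 2×2 table with both discordant counts.
- In SAP 3.2, state whether the first secondary endpoint is scored met or not met.
- Make the same deletion in Protocol 7.2. The SAP can be corrected first without departing from the protocol, because McNemar's test alone is already within the protocol's wording. SAP 5.6 gives the route for an SAP amendment before analysis; Protocol 10.3 requires an amendment and IRB review for the protocol text.
- As a minor addition, footnote the number of subjects with a 0 cc baseline V35 and show their absolute change in cc.

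The cost is a few sentences and a few lines of code, with no new data. The price of the exact version is larger p-values: at six pairs it falls below 0.05 only if all six subjects switch the same way (2 × 0.5⁶ = 0.031). The discordant counts will therefore carry most of the information.

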3.1 Primary Effectiveness Endpoint

The primary effectiveness endpoint (feasibility) will be Technical Success rate. Technical Success is defined as the administration and visualization (with TraceIT Visibility Score 2 or higher on post-TraceIT CT) of the TraceIT hydrogel between the head of pancreas and the duodenum. Technical Success rate is calculated as the proportion of subjects who are Technical Success in the intent-to-treat (ITT) population.

3.1.1 Hypotheses

This is an early feasibility study with an intent to collect information on the procedural characteristics and safety for TraceIT administration within the peri-duodenal space. Therefore, no formal hypothesis tests of primary or secondary effectiveness endpoints have been planned.

3.1.2 Sample Size

No formal hypothesis or sample size estimation has been established since this is an early feasibility study with an intent to collect information concerning the procedural characteristics and safety for TraceIT administration within the peri-duodenal space. Six (6) subjects should provide sufficient experience to allow for evaluation of procedural safety and to estimate the impact of space creation on duodenal radiation doses.

3.1.3 Statistical Methods

The proportion of TraceIT treated subjects in whom Technical Success has been achieved will be reported in ITT population, together with an exact (Clopper-Pearson) 95% confidence interval for the true proportion. This endpoint may be summarized separately also for the localized (resectable, BRPC and LAPC) subjects.

All practical monitoring and follow-up steps will be taken to ensure complete and accurate data collection. Due to the fact that subjects are undergoing therapy consistent with standard medical practices, it is anticipated that there will be minimal missing data. There will be no imputation of missing outcome data.

3.2 Secondary Effectiveness Endpoint

The secondary effectiveness endpoints of this study are the radiotherapy benefits evaluated by comparing treatment planning performed at the baseline and post TraceIT administration, which include:

- Ability to maintain safe duodenal dose constraints
- Percent/volume of GTV/PTV receiving prescription dose
- Overall duodenal dose/ dose distribution.

3.2.1 Statistical Methods

Radiotherapy Benefits will be assessed via comparison RT planning performed at baseline and post-TraceIT administration for MITT and PP population. For both scans, summary descriptive statistics will be presented by assessment (i.e., Pre- vs. Post-TraceIT Administration) for all target volume and dose constraint measurements. The GTV/PTV receiving prescription dose pre- and post-TraceIT will be reported in an additional table. For the post-TraceIT procedure data, the relative reduction from baseline in dose (V15, V20, V35, mean and maximum duodenal dose, etc.) to the duodenum will also be calculated and summarized.

For continuous radiotherapy benefit variables, the paired sample t-test will be used to test for a difference in means between treatment plans.

3.3 Exploratory Effectiveness Endpoint

The exploratory effectiveness endpoints are defined as:

- Incidence of resection
- Histology of duodenal tissues when resection is performed
- Incidence of acute (within 3 months) and late (>3 months) duodenal toxicity (for unresected subjects)
- Theoretical dose escalation from post-TraceIT treatment plan
- TraceIT persistence (at 6-months post-TraceIT in nonresected subjects)
- Change from baseline in EORTC QoL (QLQ-C30) and QLQ-PAN26
- Comparability of visualization of the fiducial marker and TraceIT hydrogel using a standardized visualization score
- Progression free and overall survival through follow-up

3.3.1 Statistical Methods

The proportion of resected subjects in the MITT or PP population, localized (resectable, BRPC or LAPC) subgroup may be calculated with an exact (Clopper-Pearson) 95% confidence interval for the true proportion, when appropriate.

The incidence of acute (within 3 months) and late (>3 months) duodenal toxicity for unresected subjects will be reported by CTCAE grade and timing.

Histology of duodenal tissue (Duodenum Damage Score) will be summarized for those subjects when resection is performed.

The summary of theoretical dose escalation from post-TraceIT treatment plan, and , migration and stability at 2-6 weeks post-TraceIT, TraceIT persistence at 6-months post-TraceIT in non-resected subjects will be presented in separated table. The pre-TraceIT and post-TraceIT duodenal space measured by site during index procedure and/or by independent assessors will be summarized separately. Average duodenal space will be

calculated if the measurements were taken from multiple observation points or duplication.

The EORTC QLQ-C30 is a questionnaire developed to assess the quality of life of cancer patients. The pancreatic cancer module QLQ-PAN26 is intended for patients at all disease stages undergoing surgical resection, palliative surgical intervention, endoscopic palliation or palliative chemotherapy. Changes in Quality of Life Measures as assessed overall and subdomains (scales) of the EORTC-QLQ-C30 and QLQ-PAN26 will be evaluated.

The five functional scales (physical, role, emotional, cognitive and social), three symptom scales (fatigue, nausea & vomiting and pain), a global health status/QOL scale, and six single items (dyspnea, insomnia, appetite loss, constipation, diarrhea and financial difficulties) from EORTC-QLQ-C30 will be summarized according EORTC QLQ-C30 Scoring Manual third edition.

The fifteen symptom items and two functional scales from QLQ-PAN26 will be analyzed according EORTC QLQ-PAN26 Scoring Manual 2.2.

Those analysis will be repeated by localized (resectable, BRPC and LAPC), as well as resected and unresected subgroup, if applicable. Scores will be compared to baseline using either a paired t-test or Wilcoxon Signed-Rank test when appropriate.

The result of comparability of visualization of the fiducial marker and TraceIT hydrogel will be summarized using a standardized visualization score for all subjects injected with TraceIT Tissue Spacer.

The following definitions will be used for Progression-Free Survival (PFS) and Overall Survival (OS) analysis:

- Progression-Free Survival (PFS): defined as the interval between the start of induction chemotherapy (prior to RT) to the earliest treatment failure (local, regional or distant progression) onset date or death (in months). Treatment failure events will be reported as SAE and adjudicated by CEC.
- Overall Survival (OS): defined as the interval between the start of induction chemotherapy (prior to RT) to death (in months).

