	Section 9.1.1	
All Adverse Events (AE) and intervening illnesses must be documented throughout the study.
 
Changed to
 
All Adverse Events (AE) must be documented throughout the study.
	Removing redundancy

	Section 9.1.1	
All adverse events, regardless of severity or relationship to investigational device, will be collected from the time of TraceIT hydrogel injection and through the 18-month visit.
 
Changed to
 
All adverse events, regardless of severity or relationship to investigational device, will be collected from the time of initiation of fiducial marker placement and through the 18-month visit.
	Further clarification of protocol for consistency
	Section 9.1.2	
The CEC will be charged with the following responsibilities:
 
 Continuous review and validation of all adverse events that occur over the course of the study and the subsequent classification of these adverse events as related to the device, or procedure. 
Changed to
 
The CEC will be charged with the following responsibilities:
 
 Continuous review and validation of all adverse events that occur over the course of the study and the subsequent classification of these adverse events as related to the device, procedure, radiotherapy, or other. 	Further clarification of protocol for consistency
	Appendix C: Sample Informed Consent	
You will receive 5 treatments every other day over a period of about 2 weeks.
 
Changed to
	Clarification of radiation therapy

		You will receive radiation therapy as per the institutional standard that will be explained to you by your doctor.	
	Appendix C: Sample Informed Consent	
You will receive radiation treatment for about 2 weeks. During this period, you will receive 5 treatments based on a schedule given to you by your doctor.
 
Changed to
 
You will receive radiation treatment for about 2 – 6 weeks. During this period, you will receive radiation treatments based on a schedule given to you by your doctor.
	Clarification of radiation therapy

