6.4.8 Post-injection RT Planning (less than 28 days following Index Procedure)

The following assessments will be performed during the post-injection RT planning:

- Repeat CT Planning Imaging using the same number of beams and set-up as Pre-injection planning
- Dosimetric data to be collected include: V5 (volume (cc) of the duodenum receiving 5 Gy or more), V10, V15, V20, V25, V30, V35, V40, duodenal mean/maximum doses, GTV/PTV minimum/mean/maximum doses as well as GTV/PTV volume, and total duodenal volume.
- Theoretical dose escalation (maximum dose to GTV while maintaining duodenal dose constraints)
- TraceIT Hydrogel and Fiducial Visibility Scoring: Visibility of the TraceIT hydrogel and the fiducial markers will be scored as follows: 1 – not visualized; 2 – faint or trace visibility (shadow or haze); 3 – visibility but indistinct borders (definable entity, not just haze); 4 – partially distinct border, partial haze; and 5 – clearly visualized, unequivocal.

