6.4.9 RT Initiation

RT must be initiated NLT 28 days following TraceIT administration. RT should be initiated NST 1 week from last chemotherapy dose. At the initiation of each fraction, the appearance of the TraceIT hydrogel with respect to presence and material distribution should be compared to RT planning CT.

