6.4.11 Week 2-6 Following Completion of RT (Restaging & Evaluation for Potential Resection)

The following assessments are to be performed at week 2-6 following completion of RT (Restaging and Evaluation for Potential Resection). These assessments can be performed at the time the subject returns for the restaging CT:

- Physical Examination: including sitting blood pressure, pulse, temperature, weight, anticoagulation status, Zubrod Performance Score.
- CT for restaging (also will evaluate TraceIT Persistence)
- Assessment of duodenal focused Adverse Events documented using NCI CTCAE
- Other Adverse Events per NCI CTCAE
- Changes in concomitant medications used to treat intestinal symptoms
- CA-19-9 level
- Pancreaticoduodenectomy should be targeted to be performed within 8 weeks after the completion of RT if applicable.

Restaging and determination of resectability will be performed in accordance with the standard institutional practices.

CT's will be reviewed by a radiologist and any radiological findings suggestive of duodenal injury shall be documented and graded when possible. Duodenal perforation would be suspected if there is a retroperitoneal collection of extraluminal gas or a lack of continuity of the duodenal wall. Duodenal erosion/ulceration is suspected with edema or hematoma of the duodenal wall, intramural gas accumulations, and focal duodenal wall thickening (>4 mm) as findings of small bowel injury.

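### SAP 3.3.1 times gel migration and stability from injection, but the protocol's only 2–6 week window runs from the end of RT

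*SAP*

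**What the plan says.** SAP 3.3.1 promises a table that includes "migration and stability at 2-6 weeks post-TraceIT", alongside theoretical dose escalation and six-month persistence. It does not name the scan.

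The protocol's 2–6 week visit has a different starting point. Protocol 6.4.11 states: "The following assessments are to be performed at week 2-6 following completion of RT". The scan at that visit is listed as "CT for restaging (also will evaluate TraceIT Persistence". The Protocol Summary and Table 2 in 6.4.1 use the same post-RT anchor. So does the SAP in 5.1.7, which places the second CA-19-9 summary 2–6 weeks after RT ends. CA-19-9 and the restaging CT belong to the same visit in Protocol 6.4.11.

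Three other protocol statements bear on timing:

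- The planning CT has an upper limit only: "Post-injection RT Planning (less than 28 days following Index Procedure" (6.4.8).
- RT start also has only an upper limit counted from injection: "RT must be initiated NLT 28 days following TraceIT administration" (6.4.9).
- At each fraction, "the appearance of the TraceIT hydrogel with respect to presence and material distribution should be compared to RT planning CT" (6.4.9).

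**The concern.** The same numerals, 2–6 weeks, appear with two different zero points. The protocol counts from the last day of RT and SAP 3.3.1 counts from injection. The time to RT start and the whole RT course lie between those two dates, so the windows cannot be equivalent.

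The time label matters for a spacer because the question is how long the gel was shown to stay in place. Protocol 8.2 lists hydrogel migration as a potential risk. Protocol 8.4 relies on stability reported in other organs while acknowledging that they differ from this site. A scan taken 8 or 12 weeks after injection but tabulated as 2–6 weeks would misstate the period over which stability was observed. If the label were instead applied literally, it would be unclear which images qualify.

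**Working it through.** **Inputs, in weeks**

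- *s*, injection to RT start: 0 to 4. The upper limit is the 28 days in Protocol 6.4.9. No minimum from injection is given; the one-week rule there runs from the last chemotherapy dose.
- *d*, RT duration: not stated in the protocol body. Section 6.4.6 gives five fractions "or an equivalent biologically effective dose if >5 fractions is being delivered". The only duration found is the revised consent wording recorded in the Rev C change log: "You will receive radiation treatment for about 2 – 6 weeks". I take 2–6 weeks as an assumption and add one week as a further assumption for a short five-fraction course.
- *w*, RT completion to restaging CT: 2 to 6 (Protocol 6.4.11).

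**Formula:** weeks from injection to restaging CT, T = s + d + w.

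**Can the SAP's figure be reproduced?** T runs from 2 to 6 only if s + d = 0, meaning RT starts and finishes on the day of injection. Even with d = 0 as a limiting case, T runs from 0 + 0 + 2 = 2 to 4 + 0 + 6 = 10. The figure is not reproduced for any RT duration.

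| RT duration | Earliest T | Latest T |
|---|---|---|
| 0 weeks (limit only) | 0+0+2 = 2 | 4+0+6 = 10 |
| 1 week (assumed) | 0+1+2 = 3 | 4+1+6 = 11 |
| 2 weeks | 0+2+2 = 4 | 4+2+6 = 12 |
| 6 weeks | 0+6+2 = 8 | 4+6+6 = 16 |
| 2–6 weeks overall | 4 | 16 |

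**When would a restaging CT fall inside the SAP window?** T ≤ 6 with w ≥ 2 requires s + d ≤ 4. Any course longer than 4 weeks therefore puts every restaging CT beyond week 6. With RT starting at the 28-day limit, a 2-week course gives 4 + 2 + 2 = 8 to 4 + 2 + 6 = 12 weeks. For courses of 2–6 weeks, the overlap with the SAP window is weeks 4–6 only, and it needs a short course started soon after injection.

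**Which post-injection images could the SAP mean?**

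| Image | Weeks after injection | Purpose given in the protocol |
|---|---|---|
| Planning CT | 0 to under 4 | Dosimetry, visibility score |
| Check at each fraction | s to s + d; within 0–6 for a 2-week course, 0–10 for a 6-week course | Presence and distribution against planning CT; no data item or time point defined |
| Restaging CT | 4–16 (3–11 for a one-week course) | Restaging, persistence |
| MRI, unresected subjects | Month 6 | Gel presence |

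None is tied to 2–6 weeks after injection.

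**The case against.** The best case for leaving the SAP alone has four parts.

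1. *The restaging CT may not be the scan meant.* The protocol assigns it to persistence and does not mention migration or stability there. This stands as a caution: the link is an inference. It is a strong one, because no other assessment in the schedule has a 2–6 week window.
2. *The per-fraction check may be meant.* It compares gel presence and distribution with the planning CT, which is close to a definition of migration and stability, and for short courses much of it could fall 2–6 weeks after injection. This also stands as a possibility. The protocol, however, gives it no score, case report form item or time point, so the SAP would still have to say so.
3. *The sentence in SAP 3.3.1 is visibly broken*, with a stray conjunction and comma just before this item, so words may be missing. That argues for asking the sponsor what was intended. It does not make the printed time point usable.
4. *The harm is limited.* SAP section 3 provides subject data listings for all data, so dates could be recovered.

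A reader might go further and infer that a programmer would pull the planning CT as the one scan reliably inside the window, or would discard restaging CTs dated after week 6. The documents support neither. Protocol 6.4.8 sets no lower limit, so a planning CT may precede week 2. The SAP contains no date-window rule for scans, and 7.3 leaves programming rules to the code and table footnotes.

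**Conclusion.** The time point in SAP 3.3.1 is wrong as written: no protocol assessment is scheduled 2–6 weeks after injection, and the window it appears to borrow is counted from the end of RT. That conclusion needs no assumption about RT duration.

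The size does depend on assumptions. With RT starting 0–4 weeks after injection and lasting 2–6 weeks, the restaging CT falls 4–16 weeks after injection; for a one-week course, 3–11 weeks. The 16-week figure adds three maxima and uses a 6-week course known only from consent wording in the change log. For courses of one to two weeks the upper limit is 11–12 weeks.

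Two stronger conclusions are tempting and should not be drawn. The first is that all restaging CTs miss the SAP window: some could fall within it after a short, early course. The second is that a main performance endpoint is compromised: migration and stability are not listed among the exploratory endpoints in SAP 3.3 or the additional data in Protocol 6.1.3, and no test or decision rests on them. One exploratory descriptive summary in six subjects is affected. This is a minor correction.

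**What to change.** In SAP 3.3.1, change the time point for migration and stability to the restaging CT taken 2–6 weeks after completion of RT, and name the post-injection planning CT as the reference scan. The planning CT is the natural reference because Protocol 6.4.9 already uses it for the per-fraction comparison. If the sponsor meant the per-fraction check, the SAP should say so and state which recorded item and which fractions are summarised.

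In either case, report days from injection to the scan used for each subject, so that the period of observed stability is explicit whatever the RT schedule. Repair the broken sentence in the same edit.

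For the restaging CT this is a one-line change that needs no new visit, scan or data collection. If the per-fraction check is intended, the sponsor would first need to confirm that a usable record of it exists.
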